## 15.2 Adverse events

An AE is any untoward medical occurrence in a subject to whom an intervention has been administered, including occurrences which are not necessarily caused by or related to that intervention. An AE can therefore be any unfavourable and unintended sign, symptom or disease temporarily associated with study activities. These events will be monitored at intervals by the trial steering committee and will not be recorded separately as an AE on the CRF.

OSIRIS Protocol v2.0 20.11.2023 Page **28** of **46** 

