#### 12.7 Control

In control group hospitals, shared decision making for high-risk patients will follow current local practices. There will be no additional training or changes to care processes for these sites.

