# 15. Safety reporting

#### 15.1 General definitions

Term	Definition				
Adverse Event (AE)	Untoward medical occurrence, unintended disease or injury, or untoward				
	clinical signs (including abnormal laboratory findings) in subjects, users or				
	other persons, whether or not related to the investigational medical device				
	and whether anticipated or unanticipated.				
Adverse Device Event	Adverse event related to the use of an investigational medical device.				
(ADE)					
Device Deficiency	Inadequacy of a medical device with respect to its identity, quality, durability,				
	reliability, usability, safety or performance.				
Serious Adverse Event	Adverse event that led to any of the following:				
(SAE)	a) death				
	b) serious deterioration in the health of the subject, users, or other				
	persons as defined by one or more of the following:				
	a. a life-threatening illness or injury, or				
	b. a permanent impairment of a body structure or a body				
	function including chronic disease, or				
	c. in-patient or prolonged hospitalisation				
	d. medical or surgical intervention to prevent life-threatening				
	illness or injury, or permanent impairment to a body				
	structure or a body function				
	c) foetal distress, foetal death, a congenital abnormality, or a birth				
	defect including physical or mental impairment.				
Serious Adverse	Adverse device effect that has resulted in any of the consequences				
Device Effect	characteristic of a serious adverse event.				
Unanticipated serious	Serious adverse device effect which by its nature, incidence, severity, or				
adverse device effect	outcome has not been identified in the current risk assessment.				
(USADE)					

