## 15.3 Site investigator assessment

The Principal Investigator is responsible for the care of the participant, or in their absence an authorised medic within the research team is responsible for assessment of any event for:

- **Seriousness:** Assessing whether the event is serious according to the definitions given in sections 15.1, 15.2 and 15.3.
- Causality: Assessing the causality of all serious adverse events in relation to the study treatment according to the definition given. If the SAE is assessed as having a reasonable causal relationship with the investigational device, then it is defined as an ADE.
- **Expectedness:** Assessing the expectedness of all ADEs according to the definition given. If the ADE is unexpected (as per the risk analysis or other RSI document), then it is a USADE.
- **Severity:** Assessing the severity of the event according to the following terms and assessments. The intensity of an event should not be confused with the term "serious" which is a regulatory definition based on participant/event endpoint criteria.
  - o Mild: Some discomfort noted but without disruption of daily life
  - Moderate: Discomfort enough to affect/reduce normal activity
  - Severe: Complete inability to perform daily activities and lead a normal life

It is expected that patients undergoing major abdominal surgery will suffer medical complications, with consequences up to and including death. Only complications considered by the Chief Investigator to be related to the use of study procedures and not a typical complication of surgery should be reported as SAEs.

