# 15.4 Notification and recording of adverse events (AEs), Adverse Device Events (ADEs)

All AEs and ADEs are to be documented in the participants' medical notes or other source data documents and the CRF. Once assessed, if the AE is not defined as SERIOUS, the AE is recorded in the investigator study file and the participant is followed up by the research team.

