# 15.5 Notification and reporting of Serious Adverse Events(SAEs), and Unexpected Serious Adverse Device Events (USADEs)

All Serious Adverse Event (SAEs) and Unexpected Serious Adverse Device Events (USADEs) will be recorded in the participants' notes, the CRF, the sponsor SAE form and reported to the sponsor (administered by the Joint Research Management Office or agreed representative) and the investigational device manufacturer within 24 hours of the site becoming aware of the event (except those specified in this protocol as not requiring reporting). Nominated co-investigators (as listed) will be authorised to sign the SAE forms in the absence of the PI at the participating sites. SAEs and reportable device deficiencies must be reported from consent until the participant's last follow-up visit.

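### Sections 15.1, 15.2, 15.4 and 15.7 set conflicting adverse-event rules and, with the 15.3 filter, leave AE/SAE reports that cannot be fairly compared between arms

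*Protocol*

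**What the plan says.** All references are to the protocol.

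- **15.1** defines an AE as an untoward occurrence in subjects, users or "other persons, whether or not related to the investigational medical device". An SAE is an AE with one of the listed serious consequences.
- **15.2** gives a second definition: "An AE is any untoward medical occurrence in a subject to whom an intervention has been administered". It continues: "An AE can therefore be any unfavourable and unintended sign, symptom or disease temporarily associated with study activities". The steering committee monitors these events, and they "will not be recorded separately as an AE on the CRF".
- **15.3** directs the site assessor to 15.1, 15.2 and 15.3 together when judging seriousness. It then sets a filter on SAE reporting: "Only complications considered by the Chief Investigator to be related to the use of study procedures and not a typical complication of surgery".
- **15.4** states: "All AEs and ADEs are to be documented in the participants' medical notes or other source data documents and the CRF".
- **15.5** states: "SAEs and reportable device deficiencies must be reported from consent until the participant's last follow-up visit". It exempts events that the protocol says need no reporting.
- **15.7** asks the Chief Investigator to review periodically the non-serious AEs entered on case report forms.
- **12.6** describes the intervention as training plus the decision-support software. **12.7** says of control hospitals: "There will be no additional training or changes to care processes for these sites".

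**The concern.** A site cannot follow all of these rules at once. Whether an event counts as an AE depends on which definition is used. Whether it reaches the CRF depends on which recording rule is used. In a cluster trial, hospitals that resolve this differently add between-hospital variation. If the resolution follows arm, which 15.2 invites, they add a difference between arms that has nothing to do with the device.

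The protocol itself names the harms at issue: confusion and stress in section 5, and distress at poor forecasts in section 7.3. The trial is open (7.1), so the relatedness judgement in 15.3 is made with the arm known. No data monitoring committee is appointed, and the steering committee advises on patient safety (26.2). If AE or SAE counts by arm were shown at the end, a reader could take an artefact of the definitions for a device effect, or miss a real one.

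**Working it through.** **1. Who falls outside the 15.2 definition.** Inputs: 600 participants and 40 hospitals, about 20 per arm (sections 4, 7.2 and 8.1). Control participants = 600 × 20/40 = 300. Under 12.6 and 12.7 none of them is given the intervention, so on a literal reading nothing that happens to them is an AE under 15.2. The same holds in the intervention arm between consent and the consultation, although 15.5 starts SAE reporting at consent. Because 15.1 builds the SAE on the AE, the narrower definition would carry over to SAEs if a site used it.

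**2. Whether the next sentence of 15.2 repairs this.** It speaks of study activities, and control participants have these too (consent, questionnaires, calls). But it is worded as a consequence of the sentence before it, so it does not clearly widen the definition. The text supports both readings.

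**3. Recording.** Section 15.2 has no separate AE entry on the CRF, 15.4 requires the CRF, and 15.7 presupposes it. The first cannot be squared with the other two.

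**4. The 15.3 filter.** A complication becomes a reportable SAE only if related to study procedures. In the control arm these amount to consent, questionnaires and follow-up contacts, so a related complication is scarcely possible. The filtered count is asymmetric by arm by construction.

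**5. What can be compared between arms.** These are collected without restriction by arm: vital status at discharge, 30 and 180 days; hospital admissions at 180 days; EQ-5D-5L; Clavien-Dindo complications 30 days after surgery in operated patients; linked hospital and mortality data (12.1, 12.4, 12.9). MCS is a co-primary non-inferiority outcome.

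Its stated size can be reproduced from section 17.1 (margin 3.5, SD 11, one-sided 2.5%, 90% power, ICC 0.01, 20% loss):
- n per arm = 2 × (1.960 + 1.282)² × 11² / 3.5² ≈ 208, so 416 in total.
- Analysed per hospital = 15 × 0.8 = 12. Design effect = 1 + 11 × 0.01 = 1.11.
- 416 × 1.11 = 462, against the stated 460. Then 462 / 0.8 ≈ 577, rounded up to 40 × 15 = 600.

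The trial therefore has a properly sized between-arm test of mental-health harm at 180 days.

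For complications, take the one-in-three rate cited in section 5 and ICC 0.01. Assume that a share f of 50% to 100% of participants have surgery (the share is not stated) and that none is lost at 30 days. Effective n per arm = 300f / [1 + (15f − 1) × 0.01]. The 95% half-width for the difference = 1.96 × √[2 × (1/3)(2/3) / effective n].
- f = 0.5: 50 patients with complications per arm; effective n = 150/1.065 = 141; half-width 11 percentage points.
- f = 1: 100 per arm; effective n = 300/1.14 = 263; half-width 8 percentage points.

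That comparison is imprecise but possible.

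**6. What these outcomes miss.** The SF-12 is taken at baseline and 180 days only (12.1). The post-clinic EQ-5D-5L is listed as predicted, not current, quality of life (12.4). The 30-day contact covers operated patients only, a group formed after randomisation by a decision that the device may influence. Distress in the weeks after the consultation, above all in patients who do not have surgery, therefore depends largely on AE reporting.

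**The case against.** The strongest defence is that section 15 is device vigilance. Only one arm has a device, so asymmetric reports are expected. Section 17 plans no between-arm AE analysis, and any tabulation may be left to the SAP. The steering committee does not see results by arm during the trial (12.10). Section 15.1 already covers every subject, and the exemption in 15.5 makes room for the 15.3 filter, so those two need not conflict.

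Much of this stands. The 15.3 filter is legitimate as vigilance, and the start of SAE reporting at consent is compatible with 15.1. But vigilance does not explain two AE definitions that sites must apply together, or opposite instructions about the CRF.

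A reader might infer more than the protocol supports:
- *That harm cannot be compared between arms at all.* This is wrong, because the outcomes in step 5 are collected in both arms and MCS is formally tested.
- *That almost only intervention-arm participants can generate AEs.* This is too strong, given 15.1 and the study-activities wording. It fits the 15.3 filter better.
- *That one can predict the imbalance*, for example 300 × 1% to 5% = 3 to 15 background events against a structural zero. The rate is an assumption with no basis in the protocol. A site following 15.2 enters no separate AE on the CRF in either arm, and the 15.3 filter would screen out unrelated background events in the intervention arm too.

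**Conclusion.** The point holds for AE and SAE reports. Two definitions and two recording rules conflict, and with the 15.3 filter the reports cannot support a fair comparison between arms. The literal reach of 15.2 is about 300 of 600 participants excluded, plus pre-consultation events in the other arm. That rests on reading the word intervention as 12.6 and 12.7 use it. No number of misclassified events can be derived from the protocol.

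The point does not extend to harm in general. The remaining gap is early distress after the consultation, which the outcomes common to both arms capture poorly.

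**What to change.** - Remove the definition in 15.2 and refer to 15.1, stating that it applies to every consented participant in both arms from consent to the 180-day contact.
- Reconcile 15.2 with 15.4 and 15.7 into one CRF recording rule used at all hospitals. Without this step, changing the definition alone could leave nothing to tabulate.
- State that SAEs passing the 15.3 relatedness filter are device vigilance data, and that any between-arm comparison of harm rests on events and outcomes recorded identically in both arms.

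There is no need to redefine relatedness around the usual-care consultation. The cost is a wording amendment and a little extra recording at control hospitals.

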## 15.3 Site investigator assessment

The Principal Investigator is responsible for the care of the participant, or in their absence an authorised medic within the research team is responsible for assessment of any event for:

- **Seriousness:** Assessing whether the event is serious according to the definitions given in sections 15.1, 15.2 and 15.3.
- Causality: Assessing the causality of all serious adverse events in relation to the study treatment according to the definition given. If the SAE is assessed as having a reasonable causal relationship with the investigational device, then it is defined as an ADE.
- **Expectedness:** Assessing the expectedness of all ADEs according to the definition given. If the ADE is unexpected (as per the risk analysis or other RSI document), then it is a USADE.
- **Severity:** Assessing the severity of the event according to the following terms and assessments. The intensity of an event should not be confused with the term "serious" which is a regulatory definition based on participant/event endpoint criteria.
  - o Mild: Some discomfort noted but without disruption of daily life
  - Moderate: Discomfort enough to affect/reduce normal activity
  - Severe: Complete inability to perform daily activities and lead a normal life

It is expected that patients undergoing major abdominal surgery will suffer medical complications, with consequences up to and including death. Only complications considered by the Chief Investigator to be related to the use of study procedures and not a typical complication of surgery should be reported as SAEs.

# 15.4 Notification and recording of adverse events (AEs), Adverse Device Events (ADEs)

All AEs and ADEs are to be documented in the participants' medical notes or other source data documents and the CRF. Once assessed, if the AE is not defined as SERIOUS, the AE is recorded in the investigator study file and the participant is followed up by the research team.

# 15.5 Notification and reporting of Serious Adverse Events(SAEs), and Unexpected Serious Adverse Device Events (USADEs)

All Serious Adverse Event (SAEs) and Unexpected Serious Adverse Device Events (USADEs) will be recorded in the participants' notes, the CRF, the sponsor SAE form and reported to the sponsor (administered by the Joint Research Management Office or agreed representative) and the investigational device manufacturer within 24 hours of the site becoming aware of the event (except those specified in this protocol as not requiring reporting). Nominated co-investigators (as listed) will be authorised to sign the SAE forms in the absence of the PI at the participating sites. SAEs and reportable device deficiencies must be reported from consent until the participant's last follow-up visit.

#### 15.6 Device deficiencies

All device deficiencies will be recorded on the Clinical investigation device deficiency log and where appropriate in the participant's medical records. Device deficiencies which could have caused a Serious Adverse Device Event must be reported to the sponsor within 24 hours of becoming aware of the event by submitting a Device Reporting Form to [contact]. Device deficiencies must be recorded and reported throughout the Clinical Investigation.

#### 15.7 Sponsor medical assessment

Sponsor has delegated the responsibility for oversight of investigational device safety profile and medical assessment of safety events to the Chief Investigator as medical assessor. The CI must review all SAEs and reportable device deficiencies within 72 hours of receipt. This review should encompass seriousness, relatedness, and expectedness. Day 0 for all USADEs is when the USADE is received by the Chief Investigator and / or coordinating team and / or sponsor (whichever is first). It is noted that the Chief Investigator cannot downgrade the PI assessment of an event's causality. If there is disagreement between Chief Investigator and Principal Investigator assessment, no pressure should be placed on the Principal Investigator to alter their assessment, but the Chief Investigator can liaise with the site Principal Investigator before the CI's final decision. The Chief Investigator and Principal Investigator assessment can differ. The Chief Investigator must also maintain oversite of non-serious AEs reported on the case report forms and review them periodically to confirm agreement.

## 16. Annual reporting

#### 16.1 Annual progress report

The APR will be written by the Chief Investigator (using the HRA's template) and submitted to the Sponsor for review prior to submission to the REC. The APR is due within 30 days of the anniversary date of the "favourable opinion" letter from the REC.

## 17. Statistical and data analysis considerations

## 17.1 Sample size calculation

The sample size calculation is considering both primary endpoints individually. The unit of randomisation is hospitals and an intra-cluster correlation of 0.01 within hospitals is assumed for each outcome. Furthermore 20% loss to follow-up at the individual participant level is assumed at the primary outcome time point of 180 days. No clusters are anticipated to drop out. For the non-inferiority comparison of the MCS a noninferiority margin of 3.5 points is chosen. A standard deviation (sd) of 11 is assumed for MCS [75] which means that the margin corresponds to approximately 30% of the sd. Accounting for clustering, 460 participants would be needed to demonstrate noninferiority with 90% power and a one-sided 2.5% significance level if there truly is no difference in MCS between groups. This equates to a recruitment target of 40 hospitals recruiting 15 participants each after accounting for loss to follow-up, i.e. 600 in total. The minimum clinically relevant difference on the DRS is a 7.5 point between-group difference in mean scores. The literature suggests a standard deviation of 16 for DRS [67] which means that the 7.5 point difference corresponds to a small to medium effect size. With the sample size required for the non-inferiority comparison and again accounting for clustering this difference can be detected with 99.8% power at the 5% significance level for a two-sided superiority test. The overall power to reject the null hypotheses for both primary outcomes is at least 89.8%.

## 17.2 Statistical analysis

The statistical analysis plan (SAP) is the principal document guiding the statistical analysis and describing it in full. All signed off versions of the SAP will be made available in a publicly accessible location. The trial statistician will not receive the treatment allocation code until after the SAP is finalised and the trial database is locked and ready for analysis. Reporting of statistical analysis results will be compliant with the CONSORT extension for Cluster Randomised trials and a CONSORT Flow diagram will

OSIRIS Protocol v2.0 20.11.2023 Page **31** of **46** 

be produced. The statistical analysis will be carried out using Stata v17.0 or later and the following general analysis principle will apply:

- For each analysis the number of patients included in the analysis, a summary measure of the outcome in each treatment group, treatment effect, 95% confidence interval and a two-sided p-value will be presented
- A significance level of α=0.05 is used throughout
- No adjustment for multiple testing of (secondary) outcomes is made
- No interim analyses are prospectively planned
- Secondary outcomes will be analysed with the same analysis model and covariates as the primary outcomes (see 18.6).

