## 6.2 Secondary outcome measures

- The SF-12 PCS Score at 180 days after the index decision making episode.
- Patient satisfaction with decision making using the Shared Decision-Making Questionnaire within 48 hours of decision making [16].
- Generic health-related quality of life utility, derived from participants' EQ-5D-5L questionnaire responses at 180 days after the index decision making episode.

OSIRIS Protocol v2.0 20.11.2023 Page **12** of **46** 

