#### Baseline data

BMI category

- Laboratory data (preoperative haemoglobin, estimated glomerular filtration rate)
- Co-morbid disease including mental illness
- Quality of life according to EQ-5D-5L
- 12-Item Short Form Survey

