#### 17.4 Primary endpoint analysis

MCS and DRS are co-primary outcomes, that is, the intervention is declared clinically effective only if both primary endpoints are statistically significant. The estimand for both outcomes will be estimated using a linear mixed-effects model with a random intercept for hospital. Restricted maximum likelihood estimation with Kenward-Roger correction will be used. Models will be adjusted for the following individual level baseline covariates (without treatment by covariate interaction) to increase power: age [continuous], surgical procedure [categorical] and Charlson co-morbidity score [ordinal]. MCS will additionally be adjusted for the MCS score at baseline. Missing covariate data will be accounted for using mean imputation [17] for continuous variables and the missing indicator approach [18] for categorical variables. The strategy for accounting for intercurrent events in the analysis models is described in section 6.3 and Appendix 1. If the patient status at 180 days follow-up is 'dead' the outcome values are defined (imputed) as a neutral position on decision regret and a population median for Mental Health Component (DRS=50,

OSIRIS Protocol v2.0 20.11.2023 Page **32** of **46** 

MCS=50). Multiple imputation under missing at random assumption will be used to impute missing outcomes where the participant has not died. Values will be imputed using predictive mean matching with 10 donors and 50 imputations. The complete set of variables included in the imputation model with be specified in the SAP.

The non-inferiority comparison for the MCS will be based on a two-sided 95% confidence interval (equivalent to a one-sided 2.5% alpha level). If the lower bound of the confidence interval is greater than the non-inferiority margin of 3.5, then non-inferiority will be declared. For both co-primary outcomes, we will present a participant-average treatment effect estimate (difference in means between the two treatment groups) along with a confidence interval. The primary outcome Decision regret will be assessed using a superiority test at the conventional 5% alpha level.

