#### 17.8 Economic evaluation

Cost-effectiveness of the intervention within the 180 day follow-up will be estimated from the perspective of health and social care services. The intervention costs will include any costs associated with training, supervision and equipment and additional consultation time to deliver the intervention. Additionally, with patient consent, we will request linked data describing secondary care attendances from 180 days prior to entry into the study until the end of follow-up in the trial (i.e. Hospital Episodes Statistics datasets for inpatient admissions, outpatient, critical care and A&E attendances). We will collect further resource use data (e.g. primary care consultations, community and residential care, out-of-pocket expenses and work-time loss due to ill health) using tailored self-report questions administered at entry into the study and at final follow-up 180 days later, requesting information about the previous 180 days. All healthcare use in the OSIRIS study will be costed using NHS and national reference costs [20, 21]. For the purpose of the economic analyses, health outcomes will be measured in qualityadjusted life years (QALYs). Health-related quality of life will be estimated using data from the EQ-5D-5L questionnaire collected at baseline, post-surgical clinic visit, 30 day follow-up after day of surgery and 180 day follow-up after index decision making episode in the OSIRIS study. EQ-5D-5L utilities will be derived using the NICE Decision

OSIRIS Protocol v2.0 20.11.2023 Page **34** of **46** 

Support Unit (DSU) tariff [22] recommended in the latest NICE guidelines for health technology assessments [23]. Mean costs and QALYs between the trial arms will be compared using separate linear mixed-effects models with a random-intercept for hospital. The following baseline covariates will be adjusted for: age, surgical procedure, Charlson co-morbidity score and hospital care costs in the 180 days prior to entry into OSIRIS or EQ-5D-5L utility at entry, respectively. Missing baseline covariate data will be accounted for using mean imputation. The two-stage bootstrap approach will be used to assess the uncertainty in cost-effectiveness.

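### Read literally, the secondary-outcome rule leaves 180-day PCS and EQ-5D-5L utility unadjusted for their own baseline values, although both are collected; the cost is mainly precision.

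*Protocol*

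**What the plan says.** The rule for secondary outcomes is one bullet in Protocol section 17.2: "Secondary outcomes will be analysed with the same analysis model and covariates as the primary outcomes (see 18.6". Section 18 is about data handling and ends at 18.5, so the reference leads nowhere. The primary model is in section 17.4.

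Section 17.4 lists the covariates shared by both co-primary models as "age [continuous], surgical procedure [categorical] and Charlson co-morbidity score [ordinal". It then adds one term for one outcome: "MCS will additionally be adjusted for the MCS score at baseline". It describes the adjustment set as "individual level baseline covariates (without treatment by covariate interaction) to increase power".

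Section 6.2 names three secondary outcomes. Two are measured at 180 days: "The SF-12 PCS Score at 180 days after the index decision making episode" and "Generic health-related quality of life utility, derived from participants' EQ-5D-5L questionnaire responses at 180 days after the index decision making episode". The third is the shared decision-making questionnaire, completed within 48 hours of the decision.

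The schedule in 12.1 and the baseline list in 12.4 both include SF-12 and EQ-5D-5L before the decision; the 12.4 entry for the latter reads "Quality of life according to EQ-5D-5L". Section 6.1 explains that the SF-12 yields both PCS and MCS.

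Section 17.8 adjusts the cost and QALY models for "hospital care costs in the 180 days prior to entry into OSIRIS or EQ-5D-5L utility at entry, respectively".

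**The concern.** For a score measured at baseline and again at follow-up, its own baseline value is usually the strongest available predictor. Section 17.4 follows that practice for MCS. The rule in 17.2, taken at its word, does not extend it to PCS, which comes from the same questionnaire, or to EQ-5D-5L utility. Neither baseline PCS nor baseline utility appears in either primary covariate list.

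The sentence also has no single meaning, because the DRS and MCS models differ. Applied to PCS or utility it could mean:

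- the three common covariates only;
- those three plus baseline MCS;
- those three plus the outcome's own baseline, by analogy with MCS.

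Only the third uses the baseline data well, and the text does not say it. The cross-reference that might settle the matter is dead.

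At stake are wider confidence intervals than necessary for two secondary outcomes, no correction for any difference between arms in those scores at baseline, and a choice of covariates left open to the analyst.

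**Working it through.** **1. Which covariates apply under each reading**

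| Outcome at 180 days | Own baseline collected? | Own baseline in the model? |
|---|---|---|
| MCS (co-primary) | Yes, SF-12 | Yes, stated in 17.4 |
| PCS (secondary) | Yes, same SF-12 | Not in any stated list |
| EQ-5D-5L utility (secondary) | Yes | Only in the QALY model of 17.8, a different endpoint |
| DRS (co-primary) | No | Not applicable |

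SDM-Q-9 is a secondary outcome without a baseline, so the question does not arise for it.

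**2. The plan's own figures (section 17.1)**

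Inputs: margin 3.5, SD 11, one-sided 2.5%, power 90%, ICC 0.01, 20% loss, 40 hospitals of 15.

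- Without clustering: 2 × (1.960 + 1.282)² × 11² / 3.5² gives 208 per arm, 416 in total.
- Design effect 1 + (m − 1) × 0.01. With m = 460/40 = 11.5 it is 1.105, and 416 × 1.105 = 459.7. The stated 460 reproduces.
- 460 / 0.8 = 575, or 14.4 per hospital, rounded up to 15 × 40 = 600.
- DRS power for 7.5 points with SD 16 is 99.76% at 460, against the stated 99.8%.
- Overall power, lower bound: 0.9976 + 0.9008 − 1 = 89.8%, as stated.

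None of these figures depends on the secondary-outcome covariates.

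**3. Precision lost by omitting the own baseline**

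Let r be the partial correlation between the baseline and 180-day score, given age, procedure and Charlson score. The protocol gives no value, so r is an assumption shown as a range. With 600 × 0.8 = 480 analysed and m = 12, the design effect is 1.11, and

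SE = SD × √[(4/480) × 1.11 × (1 − r²)].

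The interval width relative to omitting the baseline is √(1 − r²). The equivalent number analysed is 480 / (1 − r²).

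| r (assumed) | Residual variance ratio | CI width ratio | Equivalent number analysed | 95% CI half-width if PCS SD = 11 | Power for 0.3 SD |
|---|---|---|---|---|---|
| 0 | 1.00 | 100% | 480 | 2.07 | 87.7% |
| 0.3 | 0.91 | 95% | 527 | 1.98 | 90.5% |
| 0.5 | 0.75 | 87% | 640 | 1.80 | 95.0% |
| 0.7 | 0.51 | 71% | 941 | 1.48 | 99.2% |

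The PCS SD of 11 is also an assumption, borrowed from MCS. The 0.3 SD difference is only a yardstick; the protocol sets no target for these outcomes.

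**4. Sensitivity to where the baseline explains variance**

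The factor 1 − r² assumes that the baseline explains between-hospital variance in the same proportion as within-hospital variance. If it explained only the within-hospital part, the variance factor would be 0.99 × (1 − r²) + 12 × 0.01, against 0.99 + 0.12 = 1.11 with no baseline term. For r = 0.3, 0.5 and 0.7 this gives 1.021, 0.863 and 0.625. The width ratios are √(1.021/1.11) = 96%, √(0.863/1.11) = 88% and √(0.625/1.11) = 75%. The picture hardly changes.

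**5. Size of chance imbalance**

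If the ICC of 0.01 also holds for the baseline score, the standard error of the difference between arms at baseline is √[(4/600) × (1 + 14 × 0.01)] = 0.087 SD. Chance imbalance of that order is to be expected. It is part of what the unadjusted standard error already allows for.

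**The case against.** **The sentence may be meant differently.** It refers to the primary outcomes in the plural, and their lists differ, so it cannot be copied unchanged onto PCS or utility. A sympathetic reader would follow the pattern of 17.4: common covariates plus the own baseline where one exists. This stands as a reason to call the rule ambiguous rather than firmly fixed. It does not remove the need to say so.

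**The SAP may settle it.** Section 17.2 calls the SAP the principal analysis document, and it is not shown. That is fair, and missing detail would not be a finding. Here, though, the protocol states a rule instead of deferring one. A SAP that follows it literally keeps the weakness, and one that adds the baselines goes beyond the text.

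**The gain may be small.** Many participants may have major surgery between the two measurements, and hip replacement aims to change physical function, so r could be low. At r = 0.3 the interval narrows by only about 5%. This stands, and is why the range starts there.

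Three stronger readings are tempting, but the documents do not support them:

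- *That imbalance is likely and biases these results.* Allocation is unstratified, by hospital, and open, so chance or recruitment-related imbalance is possible. The protocol does not say that patients are recruited only after their hospital is allocated, and it gives no ground for calling imbalance likely. Chance imbalance does not invalidate the interval, and the existing covariates may absorb part of any difference.
- *That the protocol contradicts itself on EQ-5D-5L.* QALYs over 180 days and utility at 180 days are different endpoints. The baseline measurement enters the QALY calculation, so adjusting for it there has its own rationale, and a separate health economics plan governs that analysis.
- *That the trial's conclusion is affected.* Effectiveness is declared on DRS and MCS alone, and neither model changes.

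**Conclusion.** The point holds as a matter of wording and efficiency on two secondary outcomes. On its literal reading, section 17.2 omits baseline PCS and baseline EQ-5D-5L utility from the models for those outcomes; on its kindest reading it is ambiguous and carries a dead cross-reference. Either way it does not deliver the protocol's own stated aim of adjusting for power.

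The cost is mainly precision. Own-baseline adjustment would bring the confidence interval to about 95%, 87% or 71% of its width for r = 0.3, 0.5 or 0.7. These ratios rest on an assumed partial correlation and, to a small degree, on how the baseline explains variance between hospitals. Protection against baseline imbalance in these scores is a further benefit, not the main argument. The co-primary analyses, sample size, stated power and error rates are untouched, and SDM-Q-9 is outside the point.

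**What to change.** In section 17.2, replace the bullet on secondary outcomes with:

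> Secondary outcomes use the model in 17.4 with age, surgical procedure and Charlson score; PCS is additionally adjusted for baseline PCS and EQ-5D-5L utility for baseline EQ-5D-5L utility.

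This also replaces the reference to 18.6 with 17.4. The SAP should carry the same lists.

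The cost is one sentence and one extra covariate in each of two models. Both instruments are already completed at baseline, and the mean imputation that 17.4 sets for missing continuous covariates would cover the two added scores. Making the change before the statistician receives the allocation code removes an analyst's choice that would otherwise remain open.
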